15.3 Subject Confidentiality

The sponsor and designee affirm and uphold the principle of the subject's right to protection against invasion of privacy. Throughout this trial, a subject's source data will only be linked to the sponsor's clinical trial database or documentation via a unique identification number. As permitted by all applicable laws and regulations, limited subject attributes, such as sex, age, or

date of birth, and subject initials may be used to verify the subject and accuracy of the subject's unique identification number.

To comply with ICH Guidelines for GCP and to verify compliance with this protocol, the sponsor requires the investigator to permit its monitor or designee, representatives from any regulatory authority, the sponsor's designated auditors, and the appropriate IRBs to review the subject's original medical records (source data or documents), including, but not limited to, laboratory test result reports, electrocardiogram (ECG) reports, admission and discharge summaries for hospital admissions occurring during a subject's trial participation, and autopsy reports. Access to a subject's original medical records requires the specific authorization of the subject's LAR as part of the informed consent process (see Section 15.2).

Copies of any subject source documents that are provided to the sponsor must have certain personally identifiable information removed (i.e., subject name, address, and other identifier fields not collected on the subject's eCRF).

15.4 Clinical Trial Registration, Publication and Disclosure Policy

15.4.1 Clinical Trial Registration

In order to ensure that information on clinical trials reaches the public in a timely manner and to comply with applicable law, regulation and guidance, the sponsor will, as a minimum register all clinical trials conducted in subjects that it sponsors anywhere in the world, on publicly accessible websites such as ClinicalTrials.gov, according to local requirements, before trial initiation. The sponsor contact information, along with the investigator's city, country, and recruiting status will be registered and available for public viewing.

15.4.2 Clinical Trial Results Disclosure

The sponsor's clinical trial disclosure policy aims to comply with the clinical trial data disclosure requirements of all relevant regions. The sponsor will post the results of this clinical trial regardless of outcome, on publicly accessible websites such as ClinicalTrials.gov, as required by applicable laws and/or regulations.

Completion of trial corresponds to the date on which the final subject was examined or received an intervention for the purpose of final collection of data (usually corresponds to last subject last visit [LSLV]).

In the US, submission of results information is required not later than 1 year after the completion date (referred to as the primary completion date) of the clinical trial, which is defined as the date of final data collection for the primary outcome measure.

15.4.3 Publication of Trial Results

The results of this trial are expected to be published in a peer-reviewed scientific journal. Publication of trial results will follow the sponsor's publication policies, applicable international standards and guidelines for good publication practice, applicable laws, and/or regulations.

15.5 Insurance and Compensation for Injury

Each subject in the trial must be insured in accordance with the regulations applicable to the site where the subject is participating. If a local underwriter is required, then the sponsor or sponsor's designee will obtain clinical trial insurance against the risk of injury to clinical trial subjects.

Refer to the clinical trial site agreement regarding the sponsor's policy on subject compensation and treatment for injury. If the investigator has questions regarding this policy, he or she should contact the sponsor or sponsor's designee.

APPENDIX A RESPONSIBILITIES OF THE INVESTIGATOR

Clinical research trials sponsored by the sponsor are subject to ICH GCP and all the applicable local laws and regulations.

The investigator agrees to assume the following responsibilities:

1. Conduct the trial in accordance with this protocol.
2. Personally conduct or supervise the staff that will assist in the protocol.
3. Ensure that trial related procedures, including trial specific (non-routine/non-standard panel) screening assessments, are NOT performed on potential subjects prior to the receipt of written approval from relevant governing bodies/authorities.
4. Ensure that all colleagues and employees assisting in the conduct of the trial are informed of these obligations.
5. Secure prior approval of the trial and any changes by an appropriate IRB that conforms to 21 Code of Federal Regulations (CFR) Part 56, ICH, and local regulatory requirements.
6. Ensure that the IRB will be responsible for initial review, continuing review, and approval of the protocol. Promptly report to the IRB all changes in research activity and all anticipated risks to subjects. Make at least yearly reports on the progress of the trial to the IRB, and issue a final report within 3 months of trial completion.
7. Ensure that requirements for informed consent, as outlined in 21 CFR Part 50, ICH and local regulations, are met.
8. Obtain valid informed consent from the subject's LAR who participates in the trial, and document the date of consent in the subject's medical chart. The valid ICF is the most current version approved by the IRB. Each ICF should contain a subject authorization section that describes the uses and disclosures of a subject's personal information (including personal health information) that will take place in connection with the trial. If an ICF does not include such a subject authorization, then the investigator must obtain a separate subject authorization form from the subject's LAR.
9. Prepare and maintain adequate case histories of all persons entered into the trial, including eCRFs, hospital records, laboratory results, etc., and maintain these data for a minimum of 2 years after notification by the sponsor that all investigations have been discontinued or that the regulatory authority has approved the marketing application. The investigator should contact and receive written approval from the sponsor before disposing of any such documents.
10. Allow possible inspection and copying by the regulatory authority of GCP-specified essential documents.
11. Maintain current records of the receipt, administration, and disposition of sponsor-supplied CTM, and return all unused sponsor-supplied CTM to the sponsor.

CONFIDENTIAL

12. Report AEs to the sponsor promptly. In the event of an SAE, notify the sponsor within 24 hours.
13. Review and provide a signature as approval of the content of the CSR, if needed.

CONFIDENTIAL

APPENDIX B INVESTIGATOR CONSENT TO USE OF PERSONAL INFORMATION

The sponsor will collect and retain personal information of the investigator, including his or her name, address, and other personally identifiable information. In addition, investigator's personal information may be transferred to other parties located in countries throughout the world (e.g., the United Kingdom, United States, and Japan), including the following:

- The sponsor, its affiliates, and licensing partners.
- Business partners assisting the sponsor, its affiliates, and licensing partners.
- Regulatory agencies and other health authorities.
- IRBs.

The investigator's personal information may be retained, processed, and transferred by the sponsor and these other parties for research purposes including the following:

- Assessment of the suitability of investigator for the trial and/or other clinical trials.
- Management, monitoring, inspection, and audit of the trial.
- Analysis, review, and verification of the trial results.
- Safety reporting and pharmacovigilance relating to the trial.
- Preparation and submission of regulatory filings, correspondence, and communications to regulatory agencies relating to the trial.
- Preparation and submission of regulatory filings, correspondence, and communications to regulatory agencies relating to other vaccines used in other clinical trials that may contain the same chemical compound present in the trial vaccine.
- Inspections and investigations by regulatory authorities relating to the trial.
- Self-inspection and internal audit within the sponsor, its affiliates, and licensing partners.
- Archiving and audit of trial records.
- Posting investigator site contact information, trial details and results on publicly accessible clinical trial registries, databases, and websites.

Investigator's personal information may be transferred to other countries that do not have data protection laws that offer the same level of protection as data protection laws in the investigator's own country. The investigator acknowledges and consents to the use of his or her personal information by the sponsor and other parties for the purposes described above.

## List of Abbreviations

AE	adverse event
AGE	acute gastroenteritis
ATC	Anatomical Therapeutic Chemical
CI	confidence intervals
CRF	case report form
CSR	clinical study report
DRM	data review meeting
eCRF	electronic case report form
FAS	full analysis set
GI/GII	genogroup I/genogroup 2
GI.1/GII.4	genotype I.1/genotype II.4
GII.4c	GII.4 consensus VLP
GMFR	geometric mean fold rise
GMT	geometric mean titer
HBGA	histoblood group antigen
ICH	International Council on Harmonisation
IM	intramuscular
IRT	interactive response technology
LAR	legally acceptable representative
LLOQ	lower limit of quantification
LOD	limit of detection
MAAE	medically attended adverse event
MedDRA	Medical Dictionary for Regulatory Activities
Pan-Ig	total immunoglobulin
PPS	per protocol set
PT	preferred term
Q1	first quartile
Q3	third quartile
RNA	ribonucleic acid
SAE	serious adverse event
SAF	safety set
SAP	statistical analysis plan
SD	standard deviation
SOC	system organ class
SRR	seroresponse rate
ULOQ	upper limit of quantification
VLP	virus-like particle
WHO	World Health Organization

## 1. Introduction

The purpose of this Statistical Analysis Plan (SAP) is to describe the statistical methods, data derivations, populations of analysis and data summaries employed in determining the safety and immunogenicity of intramuscular Norovirus GI.1/GII.4 bivalent virus-like particles (VLP) vaccine in healthy Japanese infants 5 months of age.

This SAP is based on the International Council for Harmonisation (ICH) E3 and E9 Guidelines and on the study protocol NOR-109 version 3.0 dated the 15 May 2023. The final version of the SAP will be approved, signed, and dated before the start of the statistical analysis.

Noroviruses have emerged as the single most significant cause of gastroenteritis in both middle-high income countries and low resource settings worldwide. Those most at risk of severe illness include the very young, the elderly, and immunocompromised individuals. Noroviruses are highly infectious, highly resistant to environmental conditions, and have multiple routes of transmission including person-to-person, food-borne, and contaminated surfaces. Noroviruses can cause acute, mild to severe illness characterized by vomiting, diarrhea, fever, dehydration, and abdominal pain, representing a significant burden to public health.

As the burden of rotavirus in children decreases due to successful rotavirus vaccination programs in infants, norovirus infections are increasingly recognized as the primary cause of AGE in many countries around the world. Currently, there is no available vaccine to counter the disease burden associated with norovirus.

Noroviruses are single-stranded, positive-sense RNA viruses that contain a non-segmented RNA genome and comprise a genetically diverse family consisting of at least 10 genogroups, 5 of which (GI, GII, GIV, GVIII, and GIX) cause human disease. Some norovirus strains drift from year to year, and although both GI and GII and numerous genotypes are reported, GII.4 causes the vast majority of norovirus cases in children worldwide.

The investigational vaccine, HIL-214 (previously called TAK-214), is being developed for the prevention of norovirus-associated AGE. HIL-214 contains GI.1 VLPs and norovirus GII.4 consensus (GII.4c) VLPs which represents a consensus sequence of 3 GII.4 strains, as antigens. Norovirus VLPs are non-infectious because they do not contain viral RNA but are immunogenic because they preserve particulate antigen conformation and structure that mimic the functional interactions of the virus with cellular receptors.

The rationale for trial NOR-109 is to evaluate the safety and immunogenicity of HIL-214 in Japanese pediatric subjects and establish whether the data obtained is consistent with that previously obtained for non-Japanese pediatric subjects, and to support the inclusion of Japanese infants in a phase 3 trial.

The composition of HIL-214 (50/150 µg GI.I/GII.4) to be used in this phase 1 trial in Japanese infants is based on the results of trial NOR-202, a phase 2 dose-finding, safety and immunogenicity trial in 839 children aged 6 weeks to <9 years. The results of trial NOR-202 show that HIL-214 is immunogenic and had an acceptable safety profile in children aged 6

weeks to <9 years for all GI.1/GII.4c VLP compositions adjuvanted with 500 µg of aluminum as Al(OH)3 as (1) a one or two-dose regimen in infants aged 6 to <12 months, and (2) as a two or three-dose regimen in infants aged 6 weeks to <6 months for the same composition.

The clinical trials for HIL-214 have so far been performed in Europe, the United States and several countries in Latin America. The incidence rate of norovirus-attributable disease in Japan is at least as high as in other developed countries with the highest rates occurring in children below the age of 5 years and hospitalization most common in very young and very old populations. The inclusion of infants (5 months [ $\pm$ 14 days] of age at the time of first trial vaccine administration) serves to compare the data obtained for infants of non-Japanese descent with Japanese infants, in alignment with the global clinical program, and to support the inclusion of Japanese infants into phase 3.

This phase 1 trial in Japan aims to assess the safety and immunogenicity of two doses of HIL 214 administered 4 to 8 weeks apart, in 21 healthy infants aged 5 months at the time of the first trial vaccine dose administration. A placebo arm is included to allow an unbiased assessment of safety and immunogenicity.

## 2. Objectives

### 2.1. Primary Objective

- To assess the safety of HIL-214 compared to placebo.

### 2.2. Secondary Objectives

- To further assess the safety of HIL-214 compared to placebo.
- To assess the immunogenicity of HIL-214.

### 2.3. Exploratory Objectives

- [REDACTED]

## 3. Investigational Plan

### 3.1. Overall Study Design and Plan

This is a phase 1, randomized, double-blind multi-center, placebo-controlled trial in Japan to evaluate the safety and immunogenicity of HIL-214 in healthy infants 5 months of age (-14/+14 days) at first trial vaccine administration.

[figure not shown]
A total of 21 subjects will be allocated to either the HIL-214 or placebo. 14 subjects will be allocated to receive one dose of HIL-214 at Visit 1 (Day 1) and one dose of HIL-214 at Visit 2 (Day 29 to Day 57). 7 subjects will be allocated to receive one dose of placebo at Visit 1 (Day 1) and one dose of placebo at Visit 2 (Day 29 to Day 57).

All subjects will be followed for solicited local and systemic adverse events (AEs) up to 7 days after each dose of trial vaccine and unsolicited AEs up to 28 days after each dose of trial vaccine.

Serious adverse events (SAEs), medically-attended AEs (MAAEs), and AEs leading to trial withdrawal will all be followed throughout the trial.

All subjects will have four blood draws: pre-dose 1 (Visit 1), pre-dose 2 (Visit 2), 28 days post-dose 2 (Visit 3), and 6 months post-dose 2 (Visit 4), to measure all anti-norovirus total immunoglobulin (pan-Ig) and histoblood group antigen (HBGA) blocking antibodies and conduct exploratory serological immunogenicity testing.

All subjects will be followed-up for 6 months after the last dose (Visit 4) for safety.

Note: Safety phone contacts will be performed 2 and 7 days after each trial vaccine dose administration.

### 3.2. Study Endpoints

Endpoint	Summary Measures
Primary Endpoints	

Occurrence and severity of solicited local reactions up to 7 days after each dose of trial vaccine.

Occurrence, severity, and relationship of solicited systemic AEs up to 7 days after each dose of trial vaccine.

Occurrence, severity, and relationship of unsolicited AEs up to 28 days after each dose of trial vaccine.

Occurrence, severity, and relationship of AEs leading to withdrawal of trial vaccine up to 56 days post-dose 1.

	
Number of, and proportion of subjects with:
 

Solicited local reactions* up to 7 days post-dose 1 and dose 2.

Solicited systemic AEs** up to 7 days post-dose 1 and dose 2.

Unsolicited AEs up to 28 days post-dose 1 and dose 2.

AEs leading to withdrawal of trial vaccine up to 56 days post-dose 1.

 
In the safety set (SAF).

Secondary Safety Endpoints	

Occurrence, severity, and relationship of AEs leading to withdrawal from the trial, SAEs and MAAEs throughout the entire trial period

	

AEs leading to withdrawal from the trial, SAEs and MAAEs throughout the entire trial period.

 
In the SAF.

Secondary Immunogenicity Endpoints	
At baseline, pre-dose 2, 28 days post-dose 2 and 6 months post-dose 2: 

HBGA blocking antibody titers.

Pan-Ig antibody titers

	

Seroresponse Rate (SRR)*** for GI.1 titers pre-dose 2 and 28 days post-dose 2

SRR*** for GII.4 titers pre-dose 2 and 28 days post-dose 2.

GI.1 Geometric Mean Titers (GMTs) at baseline, pre-dose 2, 28 days post-dose 2 and 6 months post-dose 2.

	

• GII.4 GMTs at baseline, pre-dose 2, 28 days post-dose 2 and 6 months post-dose 2.

• GI.1 Geometric Mean Fold Rise (GMFR) from baseline to pre-dose 2, 28 days post-dose 2 and 6 months post-dose 2.

• GII.4 GMFR from baseline to pre-dose 2, 28 days post-dose 2 and 6 months post-dose 2.

 
In the per protocol set (PPS). Selected analyses may be provided using the full analysis set (FAS).

Exploratory Endpoints	

- [REDACTED]
- [REDACTED]

\* Injection site pain, erythema, induration, and swelling.  
\*\* Irritability/fussiness, drowsiness, loss of appetite, fever, vomiting (number per day/severity), and diarrhea (number per day/consistency).  
\*\*\* Seroresponse is defined as at least 4-fold increase in antibody titer value from baseline.  
Baseline is defined as last measurement taken before dose 1.

### 3.3. Vaccinations

HIL-214 for injection is provided by HilleVax, Inc. in single dose 1 mL pre-filled syringes as a 0.65 mL volume (to deliver a 0.5 mL dose). The syringe contents may appear biphasic with a clear upper layer and a white precipitate.

Placebo (0.9% NaCl [saline]) for injection is provided by HilleVax, Inc. in a container allowing delivery of a 0.5 mL dose. The contents of the placebo container will appear clear and therefore, distinguishable from the vaccine.

To maintain the blind, the trial vaccine doses (HIL-214 and placebo) will be prepared and administered by the unblinded personnel according to the instructions in the pharmacy manual. The investigator or designee will be responsible for overseeing the administration of the trial vaccine according to the procedures stipulated in this trial protocol, but will not directly observe the administration of trial vaccine.

A single dose of the investigational vaccine or placebo at 0.5 mL should be administered in the anterolateral thigh by authorized personnel.

## 4. General Statistical Considerations

Continuous data will be analyzed using descriptive statistics (i.e. n, geometric or arithmetic mean, standard deviation, median, minimum, maximum, first quartile (Q1), third quartile (Q3) and 95% confidence intervals [where applicable]). Categorical data will be analyzed using the subject count and percentage in each category. For the summary statistics of all numerical

variables unless otherwise specified, minimum and maximum will be displayed to the same level of precision as reported. Mean, median, Q1 and Q3 will be displayed to one level of precision greater than the data collected. Standard deviation will be displayed to two levels of precision greater than the data collected. Any results that are below the lower limit of quantification (LLOQ) and above the limit of detection (LOD) will be imputed as the middle point between the LOD and the LLOQ. Any results below the LOD will be imputed as half the LOD. Results above the upper limit of quantification (ULOQ) will be imputed as that limit for analysis purposes.

When count data are presented, the percentage will be suppressed when the count is zero in order to draw attention to the non-zero counts. A row denoted “Missing” will be included in count tabulations where specified on the shells to account for dropouts and missing values. The denominator for all percentages will be the number of subjects in that trial arm within the analysis set of interest, unless otherwise specified.

Unless otherwise specified, baseline will be defined as the last non-missing evaluation taken before dose 1 including both scheduled and unscheduled visits. The study day will be calculated relative to dose 1:

- If assessment date is on or after the date of dose 1 then Study Day = Assessment Date – Dose 1 Date + 1.
- Otherwise, Study Day = Assessment Date – Dose 1 Date

All analyses will be conducted using SAS Version 9.4 or higher.

Unless otherwise specified (i.e., baseline) data will be summarized based on the visit name collected on the case report form (CRF) page and presented by trial arm and overall. Unscheduled visit measurements will be included in the derivation of baseline for safety analyses and included in individual subject data listings as appropriate.

95% confidence intervals (CIs) are provided as 2-sided and by displaying the lower limit and upper limit as follows (XX.X, XX.X).

If a subject receives a different vaccination than the randomized one, this will be considered as a major protocol violation. Subject’s immunogenicity data will then be analyzed “as randomized”, while safety data will then be analyzed “as treated”. If a subject receives one active dose and one placebo dose, this will be analyzed in the HIL-214 group when “after any dose” or “overall” is considered.

For the purpose of inclusion in AE tables, incomplete/missing AE start and stop dates will be imputed as follows:

Partial AE start dates will be imputed as follows:

- If only the month and year are specified, and the month and year of the first trial vaccination is not the same as the month and year of the start date, then use the 1st of the month.
- If only the month and year are specified, then set to the date of the first trial vaccine received in the same month and year. If this results in a start date after a known or partial end date, then use the 1st of the month.

- If only the year is specified, and the year of the first trial vaccination is not the same as the year of the start date, then use January 1st of the year of the start date.
- If only the year is specified, then set to the date of the first trial vaccine received in the same year. If this results in a date that is after the known end date of the AE then use January the 1st.

If the start date is completely unknown, then use the date of the first trial vaccination.

Partial AE stop dates will be imputed as follows:

- If the event is flagged as ongoing, do not impute the stop date.
- If only the month and year are specified, then use the last day of the month.
- If only the year is specified, then use December 31st of that year.
- If the stop date is completely unknown, do not impute the stop date.

Unless specified otherwise, no other imputations for missing data will be performed.

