#### **4.1. Sample Size**

A total of 21 subjects is planned to be enrolled in order to achieve enrolment of 14 subjects in the HIL-214 arm and 7 subjects in the Placebo arm.

The objective of this trial is to evaluate the safety and immunogenicity of two IM injections of HIL-214 in infants aged 5 months ( $\pm 14$  days) at first trial vaccine administration. This trial is designed to be descriptive, and therefore the sample size was not determined based on formal statistical power calculations.

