### 8.1. Immunogenicity Endpoints

The following evaluations will be performed on the Pan-Ig and HBGA assays:

- Geometric mean titer (GMT) with 95% CI, geometric SD, minimum, maximum, Q1 and Q3. at baseline (Visit 1), Visit 2 (pre-dose 2), Visit 3 (28 days post-dose 2) and Visit 4 (6 months post-dose 2). The 95% CI will be calculated based on the t distribution of the log-transformed values for GMTs, then back transformed to the original scale for presentation.
- Geometric mean fold rise (GMFR) with 95% CI at Visit 2 (pre-dose 2), Visit 3 (28 days post-dose 2) and Visit 4 (6 months post-dose 2) relative to baseline. The 95% CI will be calculated based on the t distribution of the log-transformed values for GMFRs, then back transformed to the original scale for presentation.
- Seroresponse rate (SRR) with 95% CI based on the exact Clopper-Pearson method. Seroresponse is defined as a  $\geq 4$ -fold increase at Visit 2 (pre-dose 2), Visit 3 (28 days post-dose 2) and Visit 4 (6 months post-dose 2) relative to baseline, all considered separately. SRR of GI.1, GII.4 and GI.1 and GII.4 will be analyzed.

The GMT will be calculated using the following formula:

$$10^{\left\{ \frac{\sum_{i=1}^n \log_{10}(t_i)}{n} \right\}}$$

where  $t_1, t_2, \dots, t_n$  are observed immunogenicity titers for  $n$  subjects.

The GMFR measures the changes in immunogenicity titers within subjects. The GMFR will be calculated using the following formula:

$$10^{\left\{ \frac{\sum_{i=1}^n \log_{10} \frac{v_{ij}}{v_{ik}}}{n} \right\}} = 10^{\left\{ \frac{\sum_{i=1}^n (\log_{10} v_{ij} - \log_{10} v_{ik})}{n} \right\}}$$

where, for  $n$  subjects,  $v_{ij}$  and  $v_{ik}$  are observed immunogenicity titers for subject  $i$  at time points  $j$  and  $k = 0$  (Baseline).

Boxplots of titer and fold rise for the pan-Ig and HBGA assays will be plotted. Reverse cumulative distribution curves for the pan-Ig and HBGA assays will also be plotted.

All endpoints will be summarized by both the PPS and FAS.

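### The two-tier imputation below LLOQ can score a pair of unquantifiable titers as a 4-fold seroresponse if LLOQ is at least 3 times LOD, and it distorts GMFR at any ratio, not always upward

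*SAP*

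**What the plan says.** SAP section 4 sets three substitution rules for assay results outside the quantifiable range.

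- Below the LOD: "Any results below the LOD will be imputed as half the LOD".
- Above the LOD but below the LLOQ: the result "will be imputed as the middle point between the LOD and the LLOQ".
- At the top of the range: "Results above the upper limit of quantification (ULOQ) will be imputed as that limit for analysis purposes".

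SAP section 3.2 gives the responder rule: "Seroresponse is defined as at least 4-fold increase in antibody titer value from baseline". SAP section 8.1 applies it to the pan-Ig and HBGA assays at Visits 2, 3 and 4, for GI.1, for GII.4 and for both together: "Seroresponse rate (SRR) with 95% CI based on the exact Clopper-Pearson method". The same section says "The GMFR measures the changes in immunogenicity titers within subjects" and computes GMFR as the geometric mean of the within-infant ratio to baseline.

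Neither document says how a pair of titers that are both below LLOQ is to be treated for seroresponse or fold rise, and neither plans a sensitivity analysis for the substitution. Neither gives the LOD, LLOQ or ULOQ of either assay for either antigen.

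**The concern.** The substitution rules give different values to two results that are both unquantifiable. For a GMT this is a modest matter. For a ratio to baseline it matters more, because the ratio of the two substituted values depends only on LLOQ/LOD. The assay specification, and not the infant's response, then decides whether the ratio passes 4.

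The arms are small ("14 subjects in the HIL-214 arm and 7 subjects in the Placebo arm"), so one infant moves an SRR visibly. The trial is descriptive, so the point estimates and intervals are themselves the result. Protocol section 4.2 and SAP section 1 intend them to show whether Japanese infants respond consistently with non-Japanese infants and to support their inclusion in phase 3. An SRR that depends on unstated assay limits is a weaker basis for that comparison.

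**Working it through.** **Inputs.** Substituted values: LOD/2 and (LOD + LLOQ)/2 (SAP section 4). Threshold: 4-fold (SAP sections 3.2 and 8.1). Arm sizes: 14 and 7 (SAP section 4.1). Let R = LLOQ/LOD. R is not in the documents, so a range is shown. R must exceed 1, since at R = 1 there is no band between the limits. The plan states no figure on this point that could be reproduced.

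**Step 1: fold rise assigned to each unquantifiable pair.**

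| Baseline | Later sample | Assigned fold rise |
|---|---|---|
| below LOD | below LOD | 1 |
| LOD to LLOQ | LOD to LLOQ | 1 |
| below LOD | LOD to LLOQ | [(LOD + LLOQ)/2] / (LOD/2) = 1 + R |
| LOD to LLOQ | below LOD | 1/(1 + R) |

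**Step 2: when the third row is a seroresponse.** 1 + R ≥ 4 requires R ≥ 3.

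| R | 1.5 | 2 | 2.5 | 3 | 4 | 5 | 10 |
|---|---|---|---|---|---|---|---|
| 1 + R | 2.5 | 3.0 | 3.5 | 4.0 | 5.0 | 6.0 | 11.0 |
| Seroresponse | no | no | no | yes | yes | yes | yes |

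**Step 3: size for SRR, if R ≥ 3.** This assumes that all randomized infants contribute; a smaller PPS makes each infant count for more.

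- HIL-214: 1/14 = 7.1 points. The Clopper-Pearson interval goes from 0–23.2% (0/14) to 0.2–33.9% (1/14).
- Placebo: 1/7 = 14.3 points. The interval goes from 0–41.0% (0/7) to 0.4–57.9% (1/7).

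**Step 4: size for GMFR, at any R above 1.** Compared with scoring the pair as 1-fold, one such infant among n multiplies GMFR by (1 + R)^(1/n). At R = 3 this is 4^(1/14) = 1.10 or 4^(1/7) = 1.22. The reverse pair multiplies it by 4^(−1/14) = 0.91 or 4^(−1/7) = 0.82. No threshold is needed, because 1 + R is always above 2.

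**Step 5: direction of the net bias.** This comes from an illustrative simulation. Titers are log-normal, with log10 SD 0.4 at baseline and 0.3 for the fold rise, R = 3, and no upper limit. These SDs are assumptions and are not in the documents.

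| Baseline GMT | True fold | SRR true → planned rule | GMFR true → planned rule |
|---|---|---|---|
| at LOD | 1 | 2.3% → 11.2% | 1.00 → 1.08 |
| at LOD | 4 | 50.0% → 59.6% | 4.00 → 3.65 |
| at LOD | 10 | 90.8% → 90.0% | 10.0 → 9.0 |
| 10 times below LOD | 4 | 49.9% → 20.9% | 4.00 → 1.38 |

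At R = 2 no seroresponse arose from an unquantifiable pair in any setting.

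**The case against.** The strongest reply is that everything turns on a ratio the documents do not state. If LLOQ is less than 3 times LOD for both assays and both antigens, no seroresponse can arise from two unquantifiable titers. That stands, and the point is made only in conditional form.

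A reader might infer that the plan inflates SRR and GMFR. The documents do not support that. The last two rows of the simulation show both measures biased downward, and the second row shows SRR up while GMFR falls. The reverse pair and the ULOQ cap also pull fold rises down.

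A reader might also infer that every such infant is a false responder. That does not follow either. Going from undetectable to detectable is some evidence of a rise; only its size, 4-fold or more, is unsupported. Similarly, a baseline below LOD followed by a titer exactly at LLOQ is scored as LLOQ/(LOD/2) = 2R, which reaches 4 at R = 2. That case includes a quantifiable post-dose titer and so is a different matter.

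Immunogenicity is a secondary objective, no hypothesis test is affected, and "the sample size was not determined based on formal statistical power calculations". The same rule applies in both arms, and SAP section 8 plans listings, boxplots and reverse cumulative distribution curves in which clusters at substituted values could be noticed. This limits the consequence but does not remove the gap. A common rule need not have a common effect, because the arms will differ in where their titers lie. The SAP does not say that substituted values will be flagged.

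**Conclusion.** The point holds in conditional form. Under the SAP as written, a baseline below LOD followed by a detectable but unquantifiable titer is a seroresponse whenever LLOQ/LOD is 3 or more, and nothing in either document prevents it. Each such infant is worth 7.1 points of SRR in the HIL-214 arm or 14.3 points in placebo. GMFR is affected at any ratio above 1.

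False seroresponse is most likely where the true rise is small and baseline is near the LOD, as would be expected in placebo. There it would raise the background rate and narrow the apparent difference between arms. Where true baselines lie far below the LOD, or true rises are large, the bias can be downward. How often these pairs will occur cannot be judged from the documents. The algebra and the 1/14 and 1/7 figures rest on the SAP alone; the direction results rest on the assumed log-normal settings.

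**What to change.** In SAP section 8.1, keep the planned SRR and GMT rules and pre-specify, before unblinding:

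1. A sensitivity SRR in which an infant is a responder only if the post-dose titer is at or above LLOQ and at least 4 times baseline.
2. A sensitivity GMFR and SRR in which every result below LLOQ takes one common value, for example LLOQ/2. Two unquantifiable titers then give a 1-fold rise, and a rise from unquantifiable to exactly LLOQ gives LLOQ/(LLOQ/2) = 2-fold.

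Report the LOD, LLOQ and ULOQ for each assay and antigen next to these tables, so that the reader can see whether the ratio reaches 3.

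The cost is a few sentences and some additional tables. The first analysis removes the artefact: with R = 3, baseline GMT at the LOD and no true rise, the simulated SRR is 1.6%, against 11.2% under the planned rule and 2.3% true. It also loses real responders: at a true 4-fold rise it gives 37%, against 60% planned and 50% true. It should therefore supplement the planned SRR and not replace it. Raising all baselines below LLOQ to LLOQ is not advised, because the simulated SRR in that same 4-fold setting drops to 15%.
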